14.8 Sample Size/Accrual Rate

CONFIDENTIAL

This document is confidential. Do not disclose or use except as authorized.

Following Fleming's single phase approach and with a one-sided alpha set at 0.05 and beta at 0.20 (80% power) assuming a null VGPR or better of 18% and a successful VGPR or better of 40%, we will need to accrue 30 participants. In a previous study, the combination of bortezomib, rituximab and dexamethasone induced VGPR or better of 35% [22]. If at least 10 participants are found to have a response of VGPR or better, the trial will be deemed a success and IDR will warrant further testing in patients with WM. Accounting for 10% of non-evaluable patients, the total sample size will be 33 patients. In addition, with a sample size of 33 participants, the probability of observing at least one adverse event will be 97% when the actual probability of this event is 10%.

The accrual expectation is 2-3 patients per month with a total accrual time of 12-15 months.

14.9 Stratification Factors

There will be no stratification employed in the current study.

14.10 Analysis of Secondary Endpoints

The secondary objectives of determining the impact of MYD88 and CXCR4 gene mutations, and FcγRIIIA-158 polymorphisms in predicting overall and categorical response to treatment, as well as progression-free survival, will be assessed by presenting these outcomes by mutation/polymorphism type. If there are sufficient numbers in each category, appropriate inferential statistics may be performed. These analyses would be considered exploratory in nature.

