1.3 Secondary Objectives

- To evaluate the rate of CR, partial response (PR), minimal response (MR), stable disease (SD) and progressive disease (PD)
- To evaluate the PFS, disease-free survival (DFS), time to progression (TTP), duration of response (DOR) and time to next therapy (TTNT)
- To evaluate the attainment of response, and depth of response (VGPR or better) and expression of MYD88 L265P and CXCR4-WHIM mutations in WM.
- To determine changes in MYD88 L265P burden in response to IDR in patients with WM using real-time quantitative PCR.
- To evaluate the FcγRIIIA-158 polymorphisms as surrogate markers for response to IDR in WM.

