2.4 Correlative Studies Background

2.4.1 MYD88 L265P and CXCR4-WHIM-like mutations, and FcγRIIIA-158 (CD16) polymorphisms

One of the major advances in the field of WM has been the recent discovery of a recurrent genetic abnormality, the MYD88 L265P mutation (Treon 2012). Sanger sequencing detected such mutation in tumor samples from 49 out of 54 patients (91%) with WM. Interestingly, the mutation was not detected in normal cells from WM patients and B-cells from healthy donors, and was absent or rarely expressed in cells from patients with multiple myeloma or marginal zone lymphoma. Such finding has been independently validated in subsequent studies from Italy, France the United States with prevalence rates ranging between 90-100% (Varettoni 2013; Poulain 2013; Ondrejka 2013). More recently, allele-specific PCR assays have been developed to improve the sensitivity of detection of the mutation and the quantification of the MYD88 L265P mutation burden (Xu 2013).

More recently, mutations in the CXC chemokine receptor 4 (CXCR4) gene were identified in 16 out of 55 (29%) WM patients investigated (Cao 2012). CXCR4 mutations are the second most common mutations found in WM patients. Such mutations are similar to the ones seen in patients with WHIM syndrome, an autosomal dominant genetic disorder characterized by warts, hypogammaglobulinemia, infections and myelokathexis (Hunter 2013) conferring gain of function and decreased CXCR4 internalization. In preclinical and clinical studies, CXCR4-WHIM mutations have been associated with lower responses to Bruton tyrosine kinase inhibitors (Cao 2013), but their significance in proteasome inhibitor-treated patients is not yet known.

As part of these efforts, the impact of FcγRIIIA-158 (CD16) polymorphisms as a predictor of categorical response in WM will be assessed. In previous studies by Treon et al, the presence of at least one valine at amino acid position 158 at FcγRIIIA (CD16) predicted for response to rituximab (Treon 2005b). Patients displaying either valine/valine (V/V) or valine/phenylalanine (V/F) had a four-fold higher rate of response to single agent rituximab compared to patients displaying phenylalanine/phenylalanine (F/F) alone at FcγRIIIA-158. The impact of polymorphisms at FcγRIIIA-158 on response outcome has also been validated in other indolent

CONFIDENTIAL

This document is confidential. Do not disclose or use except as authorized.

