9. STUDY CALENDAR

	Screening ≤30 days from study entry	Induction Phase q28 days +/- 3 Days*,**						Inter-phase Visit Within 4 weeks +/- 2 weeks of completion of Cycle 6 of induction	Maintenance Phase (Beginning 8 weeks +/- 2 weeks after Induction C6D1) q 8 weeks +/- 2 weeks			Off Treatment Visit within 4 weeks +/- 2 weeks of completion of all treatment or removal from trial	Follow-up Q6 months +/- 2 weeks for 2 years ⁶
		Cycles 1 and 2			Cycles 3-6				Cycles 1-6				
		D1	D8	D15	D1	D8 ⁸	D15 ⁸		D1**	D8	D15		
Dexamethasone		X	X	X	X	X	X		X	X	X		
Ixazomib		X	X	X	X	X	X		X	X	X		
Rituximab					X				X				
Informed consent	X												
Physical exam (Ht, Wt, BSA, VS)	X	X			X			X	X			X	X
History	X	X						X	X			X	X
Concurrent meds	X	X			X			X	X			X	X
ECOG Performance Status	X	X			X			X	X			X	X
CBC w/diff, platelets	X	X	X	X	X	X	X	X	X			X	X
Serum chemistry ¹	X	X	X	X	X	X	X	X	X ¹			X	X
Coagulation Profile (PT, PTT, INR)	X												
Quantitative IgM, IgA, IgG SPEP and immunofixation ²	X	X			X			X	X			X	X
Beta-2-Microglobulin	X												
B-HCG ³	X												
Hepatitis B and C Screening	X												
MYD88 L265P status bone marrow (PCR)	X							X				X	
MYD88 L265P status peripheral blood (qPCR)	X ⁷												
CXCR4 mutational status (Sanger)	X												
Adverse event evaluation	X	X			X			X	X			X	
Neuropathy Assessment	X	X			X			X	X			X	
CT scan w/ contrast Chest/Abdomen/Pelvis ⁵	X ⁴							X ⁵				X ⁵	
Bone Marrow Biopsy and Aspiration ²	X ⁴							X				X	

*: Peripheral Neuropathy questionnaire and labs do not need to be repeated if Day 1 of induction treatment within 10 days of screening. If labs are repeated on C1D1 they must be reviewed prior to study drug administration and meet eligibility.
 **: For criteria for administration of treatment see Section 6.2
 1: Comprehensive chemistry panel: Albumin, total bilirubin, BUN, creatinine, calcium, chloride, glucose, potassium, total protein, sodium, SGOT, SGPT, alkaline phosphatase, magnesium
 2: Bone Marrow Biopsy and Aspiration will be required at Screening, Interphase visit, and Off-Treatment Visit. May be Repeated at other time points to confirm a suspected complete remission and at the Principal Investigator's discretion
 3: Serum pregnancy test for women of childbearing potential
 4: If done within 90 days of screening, this will not be required at the screening visit

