10. MEASUREMENT OF EFFECT

10.1 Response Criteria

Response criteria are based on modified response criteria updated at the Third International Workshop on Waldenström's macroglobulinemia (Kimby 2006; Treon 2011).

For participants who undergo TPE (total plasmapheresis), IgM will be considered unevaluable for 4-6 weeks following the last TPE treatment. For response assessment, post-pheresis IgM values will not be considered as nadir values.

When rituximab induced IgM flare is suspected, serum IgM response will be determined to be unevaluable by the investigator and not considered to be progressive disease.

Complete Response (CR): A complete response (CR) is defined as having resolution of all symptoms, normalization of serum IgM levels with complete disappearance of IgM paraprotein by immunofixation, and resolution of any adenopathy or splenomegaly. A near CR (nCR) is defined as fulfilling all CR criteria in the presence of positive immunofixation test for an IgM paraprotein.

Very Good Partial Response (VGPR): is defined as >90% reduction in serum IgM levels.

Partial Response (PR): Partial response (PR) is defined as achieving a $\geq 50\%$ reduction in serum IgM levels.

Minor Response (MR): A minor response (MR) is defined 25-49% reduction in serum IgM levels.

Progressive Disease (PD): Progressive disease (PD) is defined as occurring when a greater than 25% increase in serum IgM and an absolute 500mg/dL increase in IgM level occurs from the lowest attained response value (except as specified above) or progression of clinically significant disease related symptom(s). When PD is suspected on the basis of increasing serum IgM, repeat of these studies within 2 ± 1 week(s) will be required to confirm PD.

Stable Disease (SD): Stable disease is defined as having < 25% change in serum IgM levels, in the absence of new or increasing adenopathy or splenomegaly and/or other progressive signs or symptoms of WM.

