14. STATISTICAL CONSIDERATIONS

14.1 Study Design/Endpoints

Following Fleming's single phase approach and with a one-sided alpha set at 0.05 and beta at 0.20 (80% power) assuming a null VGPR or better of 18% and a successful VGPR or better of 40%, we will need to accrue 23 participants. In a previous study, the combination of bortezomib, rituximab and dexamethasone induced VGPR or better of 35% [22]. If at least 9 participants are found to have a response of VGPR or better, the trial will be deemed a success and IDR will warrant further testing in patients with WM. Accounting for 10% of non-evaluable patients, the total sample size will be 26 patients. In addition, with a sample size of 26 participants, the probability of observing at least one adverse event will be 93% when the actual probability of this event is 10%. Counting 1 patient who was registered but never started, 27 patients were accrued to this study.

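### CXCR4 and FcγRIIIA-158 effects on response are to be judged only on response categories, although serum IgM is measured at every cycle; adding a prespecified log-IgM comparison is a cheap improvement

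*Combined protocol and SAP*

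**What the plan says.** - **Objectives.** Section 1.3 asks about attainment of response and "depth of response (VGPR or better) and expression of MYD88 L265P and CXCR4-WHIM mutations in WM". It also names FcγRIIIA-158 genotype as a possible marker of response.
- **Analysis.** Section 14.10 states that genotype effects "in predicting overall and categorical response to treatment, as well as progression-free survival, will be assessed by presenting these outcomes by mutation/polymorphism type". Tests are optional and depend on adequate counts per category. No test is named, and the work is labelled exploratory.
- **Categories.** Section 10.1 defines VGPR, PR and MR by percentage fall in serum IgM; VGPR "is defined as >90% reduction in serum IgM levels". CR adds symptom, immunofixation and imaging criteria. IgM is unevaluable for a period after plasmapheresis and during suspected rituximab flare.
- **Data.** The row "Quantitative IgM, IgA, IgG SPEP and immunofixation" in the Section 9 calendar is marked at screening, in the Day 1 columns of induction and maintenance, and at the interphase, off-treatment and follow-up visits.
- **Frequencies.** Section 2.4.1 reports that CXCR4 mutations "were identified in 16 out of 55 (29%) WM patients investigated" and that MYD88 L265P prevalence is 90-100%. It gives no FcγRIIIA-158 genotype frequencies.

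No analysis of IgM as a continuous value by genotype is planned.

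**The concern.** Three of the response categories are cuts of one continuous measure that the trial already records repeatedly. Cutting it discards information, and with about eight patients in the smaller CXCR4 group there is little to spare. Under a four-fold difference in VGPR or better, about 1 of 8 mutated and 9 of 18 wild-type patients would reach it. Section 14.10 may then find the counts too small and report a table only, or apply a yes/no test with low power.

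At stake is what the trial can say about CXCR4 under a proteasome inhibitor, which Section 2.4.1 describes as unknown, and about FcγRIIIA-158. For exploratory work the useful product is an effect estimate with an interval, and 14.10 promises none by genotype.

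**Working it through.** **1. The plan's own figure.** No power or sample size is given for a genotype comparison. The only sample size is for the primary endpoint, "assuming a null VGPR or better of 18% and a successful VGPR or better of 40"%, with one-sided alpha 0.05 and 80% power. The one-sample normal formula gives n = [(1.645·√(0.18·0.82) + 0.842·√(0.40·0.60)) / 0.22]² = [(0.632 + 0.412)/0.22]² ≈ 22.5. That agrees with "we will need to accrue 23 participants" in Section 14.1, and 23/0.9 ≈ 26. (Section 14.8 gives 30 and 33 from the same inputs; that is a separate matter. The 26 treated patients in 14.1 are used here.)

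**2. Group sizes.** CXCR4: 0.29 × 26 = 7.5, so about 8 v 18; with 23 evaluable, 0.29 × 23 = 6.7, so 7 v 16. MYD88 wild-type: 0 to 10% of 26, about 0 to 3 patients.

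**3. Model (assumed).** Log(IgM/baseline) is normal with equal SD in both groups, and VGPR or better is a fall below ln(0.1). The shift between groups is the difference in normal quantiles:
- 12.5% v 50%: 0 − (−1.150) = 1.15 SD. This borrows the four-fold ratio in Section 2.4.1 for FcγRIIIA-158 with single-agent rituximab.
- 18% v 40%: −0.253 − (−0.915) = 0.66 SD. This is the weaker case.

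The SD matters only for the MR cut and the ordered test. The distance from a 90% to a 25% fall is ln(0.75/0.10) = 2.015.
- Bortezomib regimen in Section 2.3 (35% VGPR or better, 96% overall): 2.015/(1.751 + 0.385) = 0.94.
- Carfilzomib regimen (7 of 31, 74% overall): 2.015/(0.643 + 0.753) = 1.44. The counts listed beside that 74% add to 1 + 6 + 9 + 1 = 17 of 31 (55%), so this SD is only indicative.

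**4. Power, two-sided 5% (assumed), 8 v 18.** Fisher and uncorrected chi-square are fully enumerated; the others are simulated (3,000 or more runs).

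| Comparison | 12.5% v 50% | 18% v 40% |
|---|---|---|
| VGPR or better, Fisher | 36% | 11% |
| VGPR or better, chi-square | 49% | 18% |
| Four ordered categories, rank test | 62-66% | about 26% |
| IgM, Wilcoxon | 72% | 30% |
| IgM, t-test | 75% | 33% |

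Yes/no power relative to Wilcoxon on IgM is 36/72 = 0.50 and 49/72 = 0.68 in the stronger case, and 11/30 = 0.37 and 18/30 = 0.60 in the weaker. Over the ordered test the gain is about 2 to 10 points; a repeat run put the weaker case at SD 1.44 nearer 1 point, which is within simulation error.

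With no genotype effect (40% in both groups), rejection rates are Fisher 2.9%, chi-square 6.3%, Wilcoxon 4.5% and t-test 4.8%. The gain from IgM therefore does not come from a liberal test.

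**5. Sensitivity.**
- 7 v 16, 12.5% v 50%: Fisher 20%, chi-square 40%, Wilcoxon 63%. Much of the gap to Fisher is discreteness.
- FcγRIIIA-158 with an assumed 13 v 13 split, 12.5% v 50%: Fisher 42%, chi-square 59%, Wilcoxon 76-78%.
- MR or better, 8 v 18, 12.5% v 50% at the VGPR cut: Fisher 10% at SD 0.94, 35% at SD 1.44.
- MYD88, 2 v 24, 1 SD shift: continuous IgM still has only about 26%.

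**The case against.** The strongest reply is that the plan commits to no inefficient test. Section 14.10 names none, the categories are ordered, and an ordered test fits the text. That stands: a reader might infer that the plan halves power for its genotype objectives, but this follows only if the comparison is made as VGPR or better, yes or no.

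Second, a reader might infer that log IgM should become the main genotype analysis. Sections 1.3 and 2.4.1 pose the question in categorical terms, VGPR or better, and cite earlier work on that endpoint. Replacing it would change the stated objective, so IgM belongs beside it.

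Third, VGPR or better includes CR, which is not a pure 90% cut. Entry needs IgM only above twice the upper limit of normal. A patient entering at 2.5 times that limit normalises with a fall of 1 − 1/2.5 = 60%. The model ignores this.

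Fourth, a reader might extend the point to MYD88 status. There the obstacle is the number of wild-type patients, which no choice of scale cures. Change in MYD88 burden is already a separate quantitative objective.

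Finally, the analyses are exploratory with no power claim, PFS by genotype is also planned, and continuous IgM reaches only about 30% in the weaker case. All true. This limits the weight of the point but does not remove the value of an estimate with an interval from data already collected.

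**Conclusion.** The point holds as a cheap improvement for CXCR4 and FcγRIIIA-158. Response by genotype is planned only in categories while the underlying IgM values go unused. For CXCR4, a yes/no comparison on VGPR or better has about half to two-thirds of the power of continuous IgM, and nearer a third for Fisher in the weaker case. Against an ordered-category test the advantage is small.

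The sizes rest on a normal shift in log IgM with equal SDs, a single 90% cut, two-sided 5% tests, a borrowed effect size for CXCR4 and an assumed split for FcγRIIIA-158. The documents give no IgM SD and no CXCR4 effect. They do not support a general halving of power, a claim about MYD88 status, or any change to the primary endpoint.

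**What to change.** In Section 14.10:

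1. Keep the overall and categorical response tables by genotype as the stated endpoint.
2. Add a prespecified exploratory analysis of log(lowest evaluable IgM / baseline IgM), using readings up to the off-treatment visit and applying the Section 10.1 exclusions for plasmapheresis and flare.
3. Compare CXCR4 mutated v wild-type, and FcγRIIIA-158 V-carrier v F/F, by a linear model with log baseline IgM as covariate, with Wilcoxon as a check. Report the ratio of geometric means with its 95% confidence interval.
4. Use an ordered test rather than a yes/no test for any categorical comparison.
5. Leave MYD88 status descriptive.

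The cost is one paragraph and a little extra analysis, with no new visits, samples or patients. An IgM ratio is less comparable with published categorical rates, which the retained tables cover.

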14.11 Evaluation of toxicity

All participants will be evaluable for toxicity from the time of their first treatment.

14.12 Evaluation of response

All participants included in the study will be assessed for response to treatment according to criteria set forth in section 10.1.

15. PUBLICATION PLAN

Any formal presentation or publication of data from this trial may be published after review and comment by Millennium Pharmaceuticals and prior to any outside submission. Millennium Pharmaceuticals must receive copies of any intended communication in advance of publication (at least fifteen working days for presentational materials and abstracts and thirty working days for manuscripts). These requirements acknowledge Millennium Pharmaceuticals' responsibility to provide peer input regarding the scientific content and conclusions of such publications or presentations. Principal Investigator/Institution shall have the final authority to determine the scope and content of its publications, provided such authority shall be exercised with reasonable regard for the interests of Millennium Pharmaceuticals and, in accord with the trial contract and

CONFIDENTIAL

This document is confidential. Do not disclose or use except as authorized.

shall not permit disclosure of Millennium Pharmaceuticals' confidential or proprietary information.

Appendix A: Performance Status Criteria

ECOG Performance Status Scale		Karnofsky Performance Scale	
Grade	Description	Percent	Description
0	Normal activity. Fully active, able to carry on all pre-disease performance without restriction.	100	Normal, no complaints, no evidence of disease.
		90	Able to carry on normal activity; minor signs or symptoms of disease.
1	Symptoms, but ambulatory. Restricted in physically strenuous activity, but ambulatory and able to carry out work of a light or sedentary nature (e.g., light housework, office work).	80	Normal activity with effort; some signs or symptoms of disease.
		70	Cares for self, unable to carry on normal activity or to do active work.
2	In bed < 50% of the time. Ambulatory and capable of all self-care, but unable to carry out any work activities. Up and about more than 50% of waking hours.	60	Requires occasional assistance, but is able to care for most of his/her needs.
		50	Requires considerable assistance and frequent medical care.
3	In bed >50% of the time. Capable of only limited self-care, confined to bed or chair more than 50% of waking hours.	40	Disabled, requires special care and assistance.
		30	Severely disabled, hospitalization indicated. Death not imminent.
4	100% bedridden. Completely disabled. Cannot carry on any self-care. Totally confined to bed or chair.	20	Very sick, hospitalization indicated. Death not imminent.
		10	Moribund, fatal processes progressing rapidly.
5	Dead.	0	Dead.

Source: Oken MM, Creech RH, Tormey DC, Horton J, Davis TE, McFadden ET et al. Toxicity and response criteria of the Eastern Cooperative Oncology Group. Am J Clin Oncol 1982; 5 (6):649-55.

CONFIDENTIAL

This document is confidential. Do not disclose or use except as authorized.

Appendix B: IDR Neuropathy Assessment Questionnaire

Screening/Off Study
Induction/Maintenance
Cycle _____ Day _____

Patient Name: _____ MRN _____

Patient Signature: _____ Date _____

Please circle one (1) number to indicate how true each of the following statements has been for you in the past 7 days.

	None	A little bit	Somewhat	Quite a bit	Very much
I have numbness or tingling in my hands	0	1	2	3	4
I have numbness or tingling in my feet	0	1	2	3	4
I feel discomfort in my hands	0	1	2	3	4
I feel discomfort in my feet	0	1	2	3	4
I have joint pain or muscle cramps	0	1	2	3	4
I feel weak all over	0	1	2	3	4
I have trouble hearing	0	1	2	3	4
I get ringing or buzzing in my ears	0	1	2	3	4
I have trouble with buttons	0	1	2	3	4
I have trouble feeling the shape of small objects	0	1	2	3	4
I have trouble walking	0	1	2	3	4

Adapted from "Neurotoxicity Assessment Tool" Millennium. Cella DF, Tulsky DS, Gary G et al. The functional assessment of cancer therapy (FACT) scale: development and validation of the general measure. J Clin Oncol 1993;11(3):570-79. Calhoun EA, Fishman A, Roland PY et al. Validity and selective sensitivity of the FACT/GOG-Ntx. Abstract 1751. 36th Annual Meeting of the American Society of Clinical Oncology, May 2000, New Orleans, LA.

CONFIDENTIAL

This document is confidential. Do not disclose or use except as authorized.
